7.0 RISK/SAFETY INFORMATION

7.1 Established Contraindications, Warnings and Precautions of GEBT

The following contraindications, warnings and precautions have been established for the ^{13}C -Spirulina GEBT in FDA-approved labeling:

- Individuals with known hypersensitivity to Spirulina, egg, milk or wheat allergens should avoid the GEBT
- Because the GEBT is an indirect multi-compartmental method of measuring gastric emptying, GEBT results may be inaccurate in individuals compromised with

significant small bowel, pancreatic, liver, and/or lung disease. Consequently, GEBT should not be administered to patients with pulmonary dysfunction (e.g. COPD) and/or small bowel malabsorption.

- Individuals with severe lactose intolerance may wish to avoid the GEBT, as the test meal contains a small amount of lactose, approximately 2.7 grams.
- The performance characteristics for individuals under the age of eighteen (18) years have not been established for this test.
- The performance characteristics for pregnant women have not been established for this test.
- False positive and false negative results can occur with this test.
- Follow the directions for collecting breath samples carefully. Errors in the timing and/or procedures for collecting breath samples may affect test results and necessitate retesting.
- The GEBT should not be performed in individuals who have taken medications known to influence the rate of gastric emptying (e.g. erythromycin, metoclopramide, opiates and anticholinergics) within three (3) days prior to testing. Individuals should stop such medications only after consulting with and obtaining approval from their attending physician or the physician ordering the test.
- Fasting serum glucose levels of diabetic subjects should be checked before administration of GEBT and the test should only be administered to subjects with a fasting serum glucose level of $<275\text{mg/dl}$.
- After 24 hours there is no residual $^{13}\text{CO}_2$ signal in the breath arising from the ^{13}C label contained in the GEBT meal; thus, the GEBT may be administered as frequently as every 24 hours.
- The GEBT should not be administered within 24 hours (or the relevant washout period) of other ^{13}C breath tests (e.g. the ^{13}C -Urea breath test for *H. pylori*).

7.2 Potential Risk to Participant Associated with this Study

This study involves the following risks:

- Allergic reactions such as rash, itching, hives or problems breathing are a possibility if the participant were unknowingly and severely allergic to the GEBT test meal ingredients. The ingredients are 100 mg Spirulina, 27 grams of dried scrambled eggs (with nonfat milk added), saltine crackers (containing wheat) and water.

Any unanticipated problems will be reported to the IRB within ten (10) calendar days of being reported.

8.0 MONITORING AND REPORTING OF ADVERSE EVENTS/SERIOUS ADVERSE EVENTS

An Adverse Event (AE) is any untoward medical occurrence in the participant associated with administration of GEBT, whether or not considered related to GEBT.

A Serious Adverse Event (SAE) is defined as any untoward medical occurrence that:

CAIRN DIAGNOSTICS	DOC No. PRO-CD-046.01
PRO: Telehealth Administration of ^{13}C -Spirulina Gastric Emptying Breath Test (^{13}C -GEBT) Usability Study	Page 19 of 23

- Results in death
- Is life-threatening
- Requires inpatient hospitalization or prolongation of existing hospitalization
- Results in persistent disability/incapacity

AE's will be reported by the participant (or, when appropriate, by a caregiver, a surrogate of the participant or the participant's legally authorized representative).

The investigator and any qualified designees are responsible for detecting, documenting and recording events that meet the definition of an AE or SAE and remain responsible for following up AEs that are serious, considered related to the GEBT test procedure or study procedures that caused the participant to discontinue the study.

8.1 Time Period and Frequency for Collecting AE and SAE Information

All AEs or SAEs will be collected from the day of each GEBT test administration until the follow-up visit as outlined in Table 3, Schedule of Activities.

In the event any serious adverse events are reported, or observed during the GEBT administration procedure, whether or not attributable to the GEBT test procedure, the event will be reported within 24 hours to the IRB and to Cairn's medical director.

The following information will be provided in writing: study protocol number, patient's identification code, date of birth, date and nature of the serious adverse event and the causality assessment. The report of an SAE will be completed and signed by the next working day.

8.2 Intensity of an Event

The intensity/severity of an event will be classified as follows:

- Mild: that is an awareness of sign or symptom, but easily tolerated
- Moderate: that is discomfort of sign or symptom, but easily tolerated
- Severe: at least partially incapacitating (or restricting usual activity)

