6.5.2 Safety of telehealth administration of ^{13}C -Spirulina GEBT

There are no more/more severe adverse events than would have been expected to occur during in-office administration of ^{13}C -Spirulina GEBT.

6.5.3 Patient ability to prepare and administer the ^{13}C -Spirulina GEBT, under the supervision of a telehealth professional, according to instructions

Greater than or equal to 90% of Patient questionnaires record no issues with meal preparation (Exhibit B, Section 4)

Greater than or equal to 90% of meal preparation steps (described in Exhibit C, section 1) were completed successfully.

6.5.4 Patient ability to complete the GEBT test request form, under the supervision of a telehealth professional, according to instructions

Errors in test request forms occur at a rate of ~16% for in-office test administration. There are no more errors in test request form completion than are routinely found in test request forms returned with GEBTs administered in office.

6.5.5 Patient ability to collect GEBT breath samples under the supervision of a telehealth professional

Missing breath samples occur at a rate of ~6% for in-office test administration. There is not a higher incidence of missing breath samples in breath samples collected via telehealth than are routinely found in breath samples returned from GEBTs administered in office.

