6.6 End of Study

- Participants may withdraw from the study at any time, without prejudice
- An authorized investigator may discontinue any test subject at any time if medically indicated or in the best interest of the individual
- Participants who do not complete all components of the testing and compliance procedures will be excluded from the statistical analysis
- Withdrawn participants may be replaced to achieve the number of subjects specified
- The trial may be terminated prematurely if, in the judgement of Cairn's Medical Director, the severity or frequency of adverse events so warrants

Each participant is considered to have completed the study when they have completed the GEBT test administrations, follow-up questionnaire and AE review follow-up and all collected breath samples have been analyzed on the ABCA GIRMS system.

The end of the study is defined as the date on which all of the participants' breath samples have been analyzed on the ABCA GIRMS, all participant's study questionnaires have been returned, and all follow-up (AE review) has been completed.

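### Section 8.2 has no intensity grade for an event that is not easily tolerated yet neither partially incapacitates nor restricts usual activity

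*Protocol*

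**What the plan says.** Protocol Section 8.2 introduces the scale as a rule for all events: "The intensity/severity of an event will be classified as follows". It lists three grades:

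- The lowest grade is worded "Mild: that is an awareness of sign or symptom, but easily tolerated".
- The middle grade keeps the same qualifier and changes only the sensation: "Moderate: that is discomfort of sign or symptom, but easily tolerated".
- The highest grade turns to function instead: "Severe: at least partially incapacitating (or restricting usual activity" (the bracket closes directly after these words).

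The protocol shows no other intensity scale and no rule for an event that falls between grades.

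Severity is used in two other places. The safety acceptance criterion in Section 6.5.2 is "There are no more/more severe adverse events than would have been expected to occur during in-office administration of" the test. Section 6.6 allows early termination if, in the medical director's judgement, "the severity or frequency of adverse events so warrants".

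**The concern.** A three-step intensity scale should give each event one grade. Here the two lower grades share one tolerability condition, and the top grade switches to a different one, functional impairment. Nothing covers an event that fails the first condition without meeting the second. The repeated phrase in the moderate line looks like text carried over from the mild line.

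The events in question are plausible in this study. Section 5.0 requires at least 15 participants who are symptomatic for gastroparesis, and the Exhibit B questionnaire gives nausea, vomiting, bloating and fullness as the symptoms. Marked nausea or bloating after the test meal can be hard to tolerate without stopping someone from doing what they would otherwise do. During the test this is harder still to judge, because Section 5.4 already keeps participants seated apart from light activities. Events are reported by the participant (Section 8.0) and reviewed at a follow-up contact that may be a phone call or an email (Section 6.1), so the grader depends heavily on the written definitions.

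What is at stake is the quality of the severity data behind the first listed study objective, safety. An event forced down to moderate understates severity, and one forced up to severe overstates it. Two graders could do opposite things with the same event and both comply with the text. A later analysis plan cannot repair this, because the grade is assigned when the event is recorded.

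**Working it through.** No arithmetic applies. The check is whether the three definitions cover every combination of the features they use.

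**Inputs, all from Section 8.2.** The definitions use three features: the sensation (awareness or discomfort), whether it is easily tolerated, and whether there is at least partial incapacity or restriction of usual activity (called impairment below).

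**Step 1. The scale as written.**

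| Sensation | Easily tolerated | Impairment | Grade under 8.2 |
|---|---|---|---|
| Awareness | Yes | No | Mild |
| Discomfort | Yes | No | Moderate |
| Either | No | No | **None** |
| Either | No | Yes | Severe |

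The third row has no grade, so the scale is not exhaustive. The first two rows show that mild and moderate remain distinct, because awareness and discomfort separate them. The fault is the missing row, not a collapse of the two lower grades.

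**Step 2. How wide the gap is.** Severe includes partial incapacity and, as an alternative, restriction of usual activity. The ungraded band is therefore limited to events that are poorly tolerated and cause neither. It does not take in everything short of full incapacity.

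**Step 3. Where severity is used.**

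| Section | Role of severity | Tied to the 8.2 grades? |
|---|---|---|
| 6.5.2, acceptance criterion | Named alongside number of events | No grade cited, no in-office distribution by grade |
| 6.6, early termination | Named alongside frequency | No grade trigger; medical director's judgement |
| 6.4.5.1, medical director's review | None; asks whether the event was more or less likely in an office | No |
| 8.0, 8.1 and 8.4, reporting and follow-up | None; rest on seriousness, relatedness, special interest or discontinuation | No |

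Severity therefore bears on two decisions, both by judgement. Section 8.2 is the only severity scale the protocol supplies for them. The review in 6.4.5.1 does not fill the gap, since it concerns likelihood by setting and not how bad the event was.

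**Step 4. Testing the repair.** If only moderate is changed, to discomfort that is not easily tolerated and without impairment, the third row is filled but the second is emptied: easily tolerated discomfort is no longer moderate, and is mild only if awareness is stretched to include discomfort. If mild is widened at the same time to easily tolerated awareness or discomfort, rows one and two become mild, row three moderate and row four severe. This takes an event that is not easily tolerated to involve discomfort by definition.

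One unlikely combination remains: easily tolerated yet restricting activity. Read literally, it meets a lower grade and severe both now and after the edit. A clause that severe takes precedence makes the grades strictly exclusive.

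**The case against.** The best case for leaving the text alone is that little depends on it. Criterion 6.5.2 does not cite the 8.2 grades and has no comparator by grade. Expedited reporting and follow-up do not use intensity. Early termination is left to judgement. Any difficulty in applying 6.5.2 consistently comes mainly from the absence of a stated in-office benchmark, which this edit would not supply. All of this stands, and it limits the consequence. It does not remove the defect: the protocol says events will be classified on this scale, and some cannot be.

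A reader might infer more than the documents support, in three ways:

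- **That every event short of incapacity is ungraded.** The severe definition already takes in partial incapacity and restricted activity, so the gap is the narrower band described above.
- **That one regraded event could decide 6.5.2.** With no grade-based threshold or comparator in that criterion, the documents do not show that a change of grade would change the outcome.
- **That only a handful of adverse events is expected, so each counts heavily.** The protocol gives no expected count. Section 3.5 reports no serious adverse events in earlier studies and no device-reportable events in more than 5,000 tests, but says nothing about non-serious events, which are the ones affected here.

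**Conclusion.** The point holds as a minor defect of wording with a real but probably modest effect. On the text of Section 8.2, an event that is not easily tolerated and neither partially incapacitates nor restricts usual activity meets no grade and must be forced into moderate or severe. The recorded severity of such events is then unreliable, and severity is one of the two things that 6.5.2 and 6.6 ask about.

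The size cannot be quantified from the protocol: it gives neither the number of events expected among the 30 to 50 participants nor their spread across grades. The conclusion rests on a literal reading of the three definitions and on the absence of any other scale or tie-break in the document. A grading convention in a training document or case report form that is not shown would reduce the practical effect, but the protocol text would still need to agree with it.

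**What to change.** Edit the mild and moderate lines of Section 8.2 together, for example:

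- Mild: awareness of, or discomfort from, a sign or symptom that is easily tolerated.
- Moderate: discomfort that is not easily tolerated but is neither partially incapacitating nor restrictive of usual activity.
- Severe: unchanged, with a note that it takes precedence where an event also fits a lower grade.

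This is a measurement definition. It alters no procedure, sample size or participant management. The cost is two lines of text and a short note, with IRB approval before implementation as Section 12.1 requires for amendments. If any events have already been graded, those recorded as mild or moderate, and any recorded as severe without noted incapacity or restriction, should be re-read against the new wording before 6.5.2 is judged.

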8.3 Relationship to Study Procedures

Adverse events will be considered associated with the study procedure if the attribution is possible, probable or very likely. The relationship can be classified as follows:

- Not related: an adverse event that is not related to the study procedure
- Doubtful: an adverse event for which an alternative explanation is more likely
- Possible: an adverse event, which might be due to the study procedure
- Very likely: an adverse event which is listed as a possible adverse reaction and cannot be reasonably explained by an alternative explanation
- Unknown: it is not possible to assign the reaction to any of the above categories because of insufficient, pending or contradictory information

CAIRN DIAGNOSTICS	DOC No. PRO-CD-046.01
PRO: Telehealth Administration of ¹³ C-Spirulina Gastric Emptying Breath Test (¹³ C-GEBT) Usability Study	Page 20 of 23

8.4 Follow-up of AEs and SAEs

After the initial AE/SAE report, Cairn's medical director will follow the participant at subsequent visits, contacts, etc. All SAEs and non-serious AEs of special interest will be followed until resolution, stabilization, the event is otherwise explained, or the participant is lost to follow-up.

If an adverse event results in withdrawal, the patient will be followed up until the cause of the event is established, if possible, and the outcome resolved, or the patient's condition stabilized.

8.5 Regulatory Reporting Requirements for SAEs

Prompt notification of a SAE is essential so that legal obligations and ethical responsibilities towards the safety of participants and the safety of a study intervention under clinical investigation are met.

Cairn has a legal responsibility to notify both the local regulatory authority and other regulatory agencies about the safety of GEBT. Cairn will comply with country-specific (U.S. FDA) and IRB-specific regulatory requirements relating to safety reporting.

9.0 STUDY OVERSIGHT

Qualified Cairn personnel specifically designated by Cairn's medical director, [name], PhD, will provide oversight of this study protocol and supervise all study activities. The designee will ensure that all personnel associated with the study are adequately trained in the study protocol and delegations of study duties will be given to the appropriately trained personnel.

Cairn Quality Assurance and Compliance personnel will ensure:

- The study protocol is being followed as approved by Cairn Diagnostics and the IRB
- Informed consent is being obtained before GEBT test administration is conducted
- Accurate, complete and current records are being maintained
- Responsibilities have not been delegated to unspecified or untrained personnel

10.0 PRODUCT STORAGE AND ACCOUNTABILITY

GEBT kits will be distributed to telehealth study participants as needed for the study. Only participants enrolled in the study may receive the GEBT kits. Upon receipt, GEBT kits must be stored at room temperature and used within two weeks of receipt.

The kits have an expiry date and should not be used beyond the expiration date displayed on the GEBT test kit box. Collected breath samples should be stored at room temperature. Kit shipping, receipt, usage or destruction will be recorded in the proper GEBT kit inventories to assure all kits are accounted for during the study.

11.0 DATA MANAGEMENT

11.1 Breath Sample Analysis

Perform sample analysis on the participants breath sample using the ABCA GIRMS system according to SOP-QC-017, Operation, Calibration and Maintenance – ABCA GIRMS. Analysis will be conducted by trained and qualified clinical laboratory personnel with verified and documented training appropriate for operation of the ABCA GIRMS systems.

11.2 Sample retention

Retain all participant breath samples collected for at least 28 days after the sample collection date recorded on the GEBT test request form.

Dispose of the samples according to SOP-CD-021, GEBT Breath Sample Accessioning and Chain of Custody.

11.3 Data Retention

Maintain data as hard copies, scan and store electronic copies on Cairn's server.

Review all data generated during execution of the protocol for completeness and accuracy in accordance with SOP-QC-030, Data Generation and Review.

11.4 Statistical Analysis

Comparisons of rates of occurrence of errors in test administration procedures between telehealth and in-office administered tests will be performed according to accepted statistical techniques.

11.5 Reporting

Collate the results of the executed protocol, including all associated data, and document the completion of the protocol in a report. The report must be approved by the same individuals who approved the associated protocol.

12.0 IRB REVIEW/ETHICS/INFORMED CONSENT

12.1 Regulatory and Ethical Considerations

This study will be conducted in accordance with this protocol and in accordance with:

- Consensus ethical principles derived from international guidelines including the Declaration of Helsinki and Council for International Organization of Medical Sciences International Ethical Guidelines
- Applicable ICH Good Clinical Practice Guidelines
- Applicable U.S. laws and regulations

This protocol, protocol amendments, Informed Consent Form and other relevant documents (e.g. advertisements) must be submitted to an IRB/IEC and reviewed and approved by the IRB/IEC before initiation of this study.

Any amendments to this protocol will be submitted for IRB/IEC approval before implementation of changes made to the study design, except for changes necessary to eliminate an immediate hazard to study participants.

12.2 Informed Consent Process

Obtain a signed consent from the participant prior to any participation in study activities. Participants may ask questions and/or withdraw from the study at any time.

A copy of the Informed Consent Form (SPEC-CD-036) must be provided to the participant.

13.0 CONFIDENTIALITY

Assign the participant a unique identifier. Any participant's data sets that are transferred to any other party will contain the identifier only; participant names or any information which would make the participant identifiable will not be transferred.

The following steps to keep information about the participant confidential, and to protect it from unauthorized disclosure, tampering or damage:

- Verbal PHI Safeguards
 - Verbal discussions regarding the participant's information will be performed in locations that are as private as possible and reasonable measures, such as lower voices or asking unauthorized personnel to step away, will be taken to assure unauthorized personnel to not overhear conversation
- Written PHI Safeguards
 - All documents are stored in Cairn's GEBT accessioning room in locked file cabinets with limited accessibility and only authorized staff have access.
 - Clinical laboratory management identifies and documents issuance of keys to personnel that may be allowed access to Participant records.
- Inform the participant that his/her personal study-related data will be used by Cairn Diagnostics in accordance with local data protection law.
- Obtain a HIPAA authorization to collect, use and disclose the study subject's personal information and protected health information as needed to conduct the study (refer to SPEC-CD-036).

14.0 INTENDED USE OF DATA

Data obtained in this study will be used to demonstrate the usability of the ^{13}C -Spirulina GEBT when administered by telehealth procedures and to confirm that the level of risk associated with telehealth administration of ^{13}C -Spirulina GEBT is not greater than that associated with administration of ^{13}C -Spirulina GEBT according to the currently approved labeling.

15.0 EXHIBITS

- A. FDA's public announcement of PMA approval of ^{13}C -Spirulina GEBT and a copy of PMA 110015 Gastric Emptying Breath Test Letter of Approval

- B. Telehealth Administration of ¹³C-Spirulina Gastric Emptying Breath Test (¹³C-GEBT) Usability Study – Patient Questionnaire to be completed at end of ¹³C-Spirulina GEBT
- C. Telehealth Administration of ¹³C-Spirulina Gastric Emptying Breath Test (¹³C-GEBT) Usability Study – Telehealth Administrator Patient Ability/Compliance Questionnaire
- D. Telehealth Administration of ¹³C-Spirulina Gastric Emptying Breath Test (¹³C-GEBT) Usability Study – Test Request Form and Breath Sample Evaluation
- E. SOP-CD-028, Telehealth Administration Procedures
- F. SPEC-CD-032, Patient Preparation Sheet

